3 STUDY DESIGN

[figure not shown]
This is a 24-month prospective, parallel arm, cluster-randomized, controlled multicenter study in veteran organ transplant recipients receiving immunosuppressant medications through the VA system. The trial will randomize 10 VA sites, 5 to standard of care and 5 to standard of care plus the intervention. The intervention consists of a pharmacist-led health services endeavor utilizing a transplant medication dashboard system that monitors and reports on potential immunosuppression-related safety issues. The study will use prospective methodology to monitor patients for 24-months following site-randomization, comparing outcomes between the intervention and control sites. Clinical outcomes that will be assessed include health care encounters (hospitalizations and ER visits), estimated health care costs, and graft and patient survival. The functionality of the dashboard system will also be assessed by analyzing the proportion of actionable alerts created by the system as well as the proportion of missing labs, proportion of alarming lab values without follow up scheduled, estimated immunosuppression adherence (using the proportion of days covered [PDC]), proportion of significant drug interactions without an immunosuppressant level and the proportion of hospital and ER visits without follow up.

The study population will consist of veteran organ transplant recipients that receive immunosuppressant medications through the VA system. Organ transplant recipients will be identified using ICD-9/10 codes from the VA electronic health record. Once identified, active medications will be queried and those receiving immunosuppressant medications to prevent rejection (tacrolimus, cyclosporine, azathioprine, mycophenolate, sirolimus, everolimus, or belatacept) will be included in the study.

The study will take place at 10 VA sites, with 5 being randomized 5 to standard of care and 5 to standard of care plus the intervention. The 10 site locations are listed in the participating sites section of this protocol. After randomization and site initiation, all intervention sites will go live on the dashboard and pharmacist-led intervention simultaneously. Following this, patients at both the intervention and standard of care sites will be prospectively monitored for 24 months, in a parallel fashion.

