7.2 Reporting Procedures

All reporting of safety concerns will occur through the IOC, as described above. The IOC will meet bi-annually and as necessary by telephone. The IOC will review reports created by the study biostatistician which incorporate clinical outcomes and SAEs, including rates of hospitalization, ED visits, graft loss and death, compared between the two groups. The recommendations of the IOC will be reviewed and the PI will take appropriate corrective actions as needed. As part of this oversight, we will also recruit an independent transplant nephrologist that is not affiliated with this study to provide their expertise and review of all study activities. This expert will conduct the following:

- 1) Review the research protocol and plans for data and safety monitoring.
- 2) Evaluate the progress of the intervention, including periodic assessments of data quality and timeliness, site enrollment and retention, participant risk versus benefit, integrity of the intervention, and other factors that can affect study outcome.
- 3) Consider factors external to the study when interpreting the data, such as scientific or clinical developments that may impact the safety of study participants or the ethics of the study.
- 4) Make recommendations to the internal IOC, IRB, and VA R&D/VA HSR&D for continuation or termination of the study.
- 5) Protect the confidentiality of study data and monitoring.

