9.3.2 Secondary outcomes

Secondary assessment will include a cost benefit analysis. Overall health care costs accrued during the 24-month study, as well as those accrued in the 24-months prior to study initiation will be analyzed and compared between the control and intervention groups. Cost data will be standardized using the VA Health Economics Resource Center (HERC) definitions, which normalizes regional differences in costs due to variation in cost of living indices. As with the primary outcome, we will also acquire and link CMS claims data to gain a comprehensive assessment of costs, including those that accrue from non-VA care (after study completion). Costs will also be sub-analyzed into three predominant categories: inpatient costs, outpatient costs and pharmacy costs, as described in the statistical analysis plan. To fully assess if the intervention is has a direct monetary benefit, we will measure costs of the intervention will include estimates of time and resources to implement the dashboard and train and support the intervention site pharmacists. Similar to primary outcome, we expect that as ER visits and hospitalizations decrease within the intervention arm, there will be a corresponding decrease in overall costs as well, predominantly driven by inpatient costs. We expect this decrease to occur during the second 12 months of the study period, as the intervention is likely to have a lag effect on this outcome as well.

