calibration (PSC).⁵⁷ We will assess the effect of the intervention on different sources of cost which include inpatient, outpatient and pharmacy in addition to the total aggregated cost. The cost models will be estimated using log-normal or gamma models (special cases of GLMM) to examine the association of the intervention with cost, adjusting for the aforementioned patient sociodemographics, donor information and transplant characteristics. Cost will be obtained from VINCI CDW and HERC as inpatient, outpatient, pharmacy and total aggregate for two years prior to the study period and for the two years of the intervention. We will also account for non-VA costs through linkage with CMS claims data. We will estimate different models adjusting for the clinical outcomes in order to examine the robustness of the results. GLMM allows for correlation between cost categories as well as for the likely skewed distribution of cost data. The Park test will be performed to check for the appropriate distribution of the cost data and AIC and BIC statistics for goodness of fit. Since, inpatient cost could exhibit a point mass of zero, we will use marginalized two-part models that are appropriate for semi-continuous data to model the relationship between the intervention and inpatient cost.^{58, 59} In general, statistical analyses will use two-sided tests with alpha set at 0.05.

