10 DATA COLLECTION AND QUALITY ASSURANCE

10.1 Data Collection and Management

There will two general types of data used for this proposal, which includes operational data used for the dashboard system and research data to assess the impact of the intervention on outcomes. Operational data for the dashboard will be captured through querying the national VA CDW operational database using the FRS environment and stored in VISN 7 space already approved and allocated for this project. These data elements include diagnoses, laboratory values, medication regimens, refill histories, provider types and health care encounters (hospitalizations, ER visits), gathered and queried on a daily basis. The pharmacists at intervention sites will access their site-specific dashboard information stored on the server through an end-user permission access link that will restrict which patients are visible to ensure appropriateness of access to the correct PHI.

For the research component of the proposal, data will be captured through the research CDW and housed within the VINCI environment. We will link the VA data to the SRTR registry and CMS claims data. The CDW will provide data to assess outcomes including hospitalizations, ER visits and costs, as well as mortality. CDW data will also be used to assess interventions by querying pharmacists' progress notes. The CMS data will provide non-VA health care utilization, including hospitalizations and ER visits, as well as non-VA cost estimates. The SRTR data will provide all baseline donor, recipient and transplant characteristics as well as clinical outcomes, including acute allograft rejection, graft loss and death. We will also capture pharmacist entered data, which will be their assessments of the dashboard system. We will deploy a web-based data entry system that the intervention pharmacists will use during the first year of the intervention to assess the dashboard functionality. Queries answered by intervention pharmacists will include the number of alerts received, how many were considered clinically relevant/actionable, time to conduct the intervention and general intervention types. This data will be captured through the use of the REDCap system.

After data is cleaned and completely ready for analysis, we will remove identifiers from the final datasets. This will minimize the risk of loss of confidentiality. All data will be stored on the VINCI system and only approved study personnel will have access to this data.

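### If the clinical outcomes include hospitalizations and ER visits, cost models adjusted for them do not test the robustness of the total cost effect

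*Combined protocol and SAP*

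**What the plan says.** The main cost models in Section 9.4 are log-normal or gamma, with a marginalized two-part model for inpatient cost. They are fitted "adjusting for the aforementioned patient sociodemographics, donor information and transplant characteristics", so no clinical outcome enters them. A few sentences later comes the additional set: "We will estimate different models adjusting for the clinical outcomes in order to examine the robustness of the results". The sentence does not say which outcomes are meant, and no rule is given for reading a change in the estimate.

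Section 9.1 states the cost hypothesis as a between-arm difference in health care costs at 24 months, which is a total effect. Section 9.3.2 gives the expected mechanism: "we expect that as ER visits and hospitalizations decrease within the intervention arm, there will be a corresponding decrease in overall costs as well", and this is to be "predominantly driven by inpatient costs".

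The term clinical outcomes is used in more than one sense:

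- Section 3: "Clinical outcomes that will be assessed include health care encounters (hospitalizations and ER visits), estimated health care costs, and graft and patient survival".
- Section 7.2 describes safety reports "which incorporate clinical outcomes and SAEs, including rates of hospitalization, ED visits, graft loss and death".
- Section 10.1, on the registry data: "clinical outcomes, including acute allograft rejection, graft loss and death".
- The exploratory paragraph of Section 9.3.2 uses it for graft and patient survival.

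**The concern.** A robustness check should aim at the same quantity under different assumptions. Encounters occur after randomization and are the plan's own explanation of how costs would fall. Putting them in the cost model changes the question from how much the intervention changes cost to how much it changes cost among patients with the same number of encounters. That second quantity can be near zero when the first is large.

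The comparison at equal encounter counts is also no longer protected by randomization. If encounters are reduced in the intervention arm, a patient there with a given count is on average frailer than a control patient with the same count. Frailty that also raises other costs then biases the adjusted contrast upwards.

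At stake is the interpretation of the secondary cost outcome and of the cost-benefit paper listed in Section 14. An attenuated estimate reported under the label of robustness invites the wrong conclusion.

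**Working it through.** **1. Inputs from the documents.** Section 9.2 gives 1.269 ED visits per person-year and a 25% relative decrease; follow-up is 24 months. The control mean is 1.269 × 2 = 2.538 and the intervention mean 0.75 × 2.538 = 1.9035.

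**2. The plan's own figure.** There is none for cost. The primary-outcome sample size shows that the 24-month mean is the one the plan used:

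- Per arm, unclustered: (1.960 + 0.842)² × (1/2.538 + 1/1.9035) / (ln 0.75)² = 87.2.
- Design effect with 1,350/10 = 135 per site and ICC 0.05: 1 + 134 × 0.05 = 7.7.
- Total: 2 × 87.2 × 7.7 ≈ 1,343, against the stated 1,350.
- After 15% loss: 1,350/0.85 ≈ 1,589, against the stated 1,600.

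The figure reproduces. It does not bear on the point beyond supporting the input.

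**3. Assumptions.** The documents give no cost mean, SD or encounter share. Let s be the encounter share of control cost (30%, 50%, 70%) and d the multiplier on all other cost in the intervention arm (1 = no saving outside encounters). The cost per encounter is the same in both arms. Patient frailty u is gamma with mean 1 and variance 1, and encounters H are Poisson given u.

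**4. Total effect.** Cost ratio = d(1 − s) + 0.75s.

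- d = 1: 0.925, 0.875, 0.825.
- d = 0.95: 0.890, 0.850, 0.810.

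**5. Effect at a fixed encounter count, frailty acting only through encounters.** Expected cost given H is d·b + cH in the intervention arm and b + cH in control, where b is other cost and c the cost per encounter. With d = 1 the ratio is exactly 1 for every H. With d = 0.95 it lies between 0.95 and 1. So the part through encounters disappears and the rest stays.

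**6. Frailty also raising other cost (in proportion to √u).** Given H, u is gamma with shape 1 + H and rate 1 + mean. At the same count, mean frailty in the intervention arm is higher by 3.538/2.9035 = 1.219, and other cost by √1.219 = 1.104. With d = 1 the adjusted ratio must therefore exceed 1.

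**7. Fitted models.** Gamma GLM with log link, 200,000 simulated patients, no site effect (this shows bias, not precision). The two adjusted columns use log(1 + H) and indicators for each count.

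| s | d | frailty raises other cost | unadjusted | adj. log(1 + H) | adj. categories |
|---|---|---|---|---|---|
| 0.3 | 1 | no | 0.922 | 0.991 | 0.997 |
| 0.5 | 1 | no | 0.876 | 0.994 | 0.999 |
| 0.7 | 1 | no | 0.825 | 0.998 | 0.998 |
| 0.3 | 1 | yes | 0.930 | 1.088 | 1.087 |
| 0.5 | 1 | yes | 0.875 | 1.079 | 1.076 |
| 0.7 | 1 | yes | 0.834 | 1.069 | 1.061 |
| 0.3 | 0.95 | no | 0.895 | 0.957 | 0.963 |
| 0.5 | 0.95 | no | 0.851 | 0.962 | 0.967 |
| 0.7 | 0.95 | no | 0.811 | 0.969 | 0.969 |

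Counting an ED visit and the admission that follows as two events, using the 48% in Section 9.2, gives a control mean of 2.538 × 1.48 = 3.756. With shares of 40%, 60% and 70% and d = 1, the ratios were 0.902, 0.852 and 0.823 unadjusted and 0.993 to 0.994 adjusted for log(1 + H). The choice of mean does not matter.

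**8. Narrow reading.** Adjusting only for a graft-loss or death indicator (assumed probability 0.02 + 0.02H, giving 7.1% in control and 5.8% in intervention), with s = 0.5 and d = 1, moved the ratio from 0.875 to 0.883. This run gives graft loss and death no cost of their own and ignores the censoring at these events in Section 9.4, so it is indicative only.

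**9. Inpatient cost.** Section 9.3.1 counts a hospitalization when there is at least one overnight stay. Having any inpatient cost is then nearly the same event as having a hospitalization, so with that covariate the zero part of the two-part model is explained almost by definition.

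**The case against.** The strongest objection is that the sentence never mentions encounters. Within Section 9.4, encounters are treated as utilization outcomes. The exploratory paragraph of Section 9.3.2 and Section 10.1 keep the term for graft loss, death and, in 10.1, rejection. The Section 3 list also contains cost itself, which cannot be a covariate in a cost model, so it cannot be carried over literally. The Section 7.2 list coincides with the SAE definition in Section 7.1 and does not settle the meaning. On the narrow reading little of the expected pathway is removed. This stands, and the conclusion has to be conditional. It does not clear the sentence: rejection, graft loss and death are also post-randomization variables, and the text leaves the broad reading open.

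Second, the near-total loss of effect follows from assuming that all savings run through encounters. That also stands. Section 9.3.2 expects inpatient cost to be the predominant driver, not the only one, and the d = 0.95 rows show that a saving by another route survives.

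Third, a reader might infer that the plan would declare the cost result non-robust and withdraw it. The documents do not say so; no rule for interpreting attenuation is given. A reader might also infer that the cost analysis as a whole is compromised. It is not: the main model uses sociodemographic, donor and transplant covariates only and still estimates the total effect.

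Finally, a model with encounters as covariates can usefully describe how far savings are explained by fewer events. That is a fair use under its own label, not as a check on the total effect.

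**Conclusion.** The point holds in conditional form. If the clinical outcomes include hospitalizations and ER visits, the additional models estimate a residual direct effect and cannot do the job the plan gives them. Under the stated assumptions a total cost ratio of 0.925 to 0.825 becomes about 1.00, and about 1.06 to 1.09 when frailty also raises other costs. With a further 5% reduction in other cost and no such frailty link, the adjusted ratio is about 0.96 to 0.97. The direction follows from the mechanism in Section 9.3.2; the size rests on assumed cost shares and frailty. If only rejection, graft loss and death are meant, the attenuation is probably small. Either way the outcomes are unnamed and the robustness label does not fit. The issue is confined to supplementary models for a secondary outcome; the primary outcome and the main cost model are untouched.

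**What to change.** Take these models out of the robustness checks in Section 9.4, in one of two ways:

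- delete the sentence; or
- name the outcomes, describe the models as a descriptive mediation (direct-effect) analysis, note that shared causes of encounters and cost may bias them, and state that attenuation is not evidence against the total cost effect.

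For robustness, use checks that keep the total effect as the target. The elements are already in the plan: gamma versus log-normal versus two-part models, different baseline covariate sets, and VA-only versus VA plus CMS costs. They only need to be named as the robustness set.

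The cost is one sentence in the SAP, with no new data and no effect on sample size or conduct. Deletion loses the description of the pathway; relabelling keeps it.

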Study Title

Improving TraNsplant Medication Safety through a Technology and Pharmacist Intervention (ISTEP)

Objectives

Primary

1. 24-month rate of hospitalization and emergency room visits compared between the intervention and usual care groups

Secondary

2. 24-month total estimated health care costs, compared between the intervention and usual care groups
3. Estimated graft survival rates, compared between the intervention and usual care groups and defined as the proportion of patients that continue to have a functioning allograft at the end of the 24-month study
4. Estimated patient survival rates, compared between the intervention and usual care groups and defined as the proportion of patients alive at the end of the 24-month study
5. Potential medication safety issues, defined as the proportion of patients with the following, based on automated reports for the transplant medication dashboard:
 - a. Percent of patients with missing labs
 - b. Percent of patients alarming lab values without follow up scheduled
 - c. Immunosuppression adherence, estimated using the proportion of days covered (PDC)
 - d. Percent of patients on significant drug interaction without a immunosuppressant level
 - e. Percent of patients with hospital discharge or ED visit without follow up scheduled
6. Proportion of alerts that were deemed clinical relevant and actionable by the intervention pharmacists
7. Proportion of interventions that were deemed to be accepted when made to other providers based on dashboard reporting information
8. Average time required to respond to each alert

Design and Outcomes

This is a 24-month, prospective, multicenter, cluster-randomized, parallel-arm, controlled clinical trial assessing the impact of a pharmacist-led technology-enabled intervention designed to improve immunosuppression medication safety

in veteran organ transplant recipients. The study includes 10 sites, five sites randomized to standard clinical care and five to standard care plus the technology-enabled pharmacist intervention.

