For the assessment of the functionality of the dashboard and the time required to complete the intervention, there will be no comparisons or modeling within this analysis; we will utilize standard descriptive statistics for these measurements, including mean (SD), median (IQR), proportion (%) and 95% confidence interval. Variables assessed for this outcome will be captured through input into the REDCap database by intervention pharmacists during the first year of the intervention. We will compile the total number of alerts the dashboard system generates at each site and assess the proportion of these that were deemed clinical relevant and actionable by the pharmacists. We will also determine the mean/median time required to complete the intervention on a daily basis and estimate the time per 100 patient days. We will conduct these assessments concurrently on a bimonthly basis for the first year of the intervention, which will allow us to modify the dashboard system's reporting thresholds and improve functionality if deemed necessary by the investigational team. We will also assess the overall functionality of the dashboard at the end of the first year to determine composite metrics. Based on our experience with the current system, after an initial bolus effect, we expect the dashboard will produce two to three new alerts per 100 patient days with one to two of these being relevant and actionable. We will utilize 95% confidence intervals actual versus expected rates.

We will handle missing data using several techniques including multiple imputation and maximum likelihood.⁶⁰ Missing data mechanisms will be examined using both univariate and multivariate methods. We will check for missing at random (MAR) by creating a missing indicator for each missing variable and study the predictors of missingness using logistic regression. If any of the fully observed covariates or outcomes becomes significant in the missing data model then we will use methods for MAR if we do not have any reason to believe that the missing data mechanism is not at random. The proposed GLMM models, which are mixed effects models for the longitudinal data analyses, can handle data that are missing at random (MAR) and provide robust estimates. For the cross-sectional data analysis plan, we will use

multiple imputation approaches and for categorical missing data we will use latent class based multiple imputation.^{57,60}

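### The standard 95% intervals planned for the dashboard measures make no allowance for five sites with one pharmacist each, or for repeated alerts within patients, and would be too narrow for the use the plan makes of them

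*Combined protocol and SAP*

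**What the plan says.** The synopsis lists among the secondary objectives "Proportion of alerts that were deemed clinical relevant and actionable by the intervention pharmacists". For dashboard functionality and pharmacist time, section 9.4 states that "there will be no comparisons or modeling within this analysis" and that "we will utilize standard descriptive statistics for these measurements, including mean (SD), median (IQR), proportion (%) and 95% confidence interval". It plans to count alerts by site: "We will compile the total number of alerts the dashboard system generates at each site". Time is summarised as the "mean/median time required to complete the intervention on a daily basis" and per 100 patient days.

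The expectation is stated numerically: "we expect the dashboard will produce two to three new alerts per 100 patient days", "with one to two of these being relevant and actionable". The intervals are then given a purpose: "We will utilize 95% confidence intervals actual versus expected rates".

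The data are entered by the intervention pharmacists during the first 12 months (section 9.3.2). Section 13 describes five such pharmacists, one per intervention site. Section 9.3.2 says the time data should let administrators judge the staffing needed if the dashboard is spread across the VA, and section 14 plans that spread.

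**The concern.** Whether an alert is relevant and actionable is the judgement of one pharmacist at one site, so alerts from a site share a rater, a patient mix and local practice. Section 5.3 says that usual care differs somewhat between the sites. Several alerts will also come from the same patient. A standard binomial or Poisson interval treats every alert as a separate, independent piece of information.

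The plan handles this elsewhere. Section 9.2 uses an ICC for the primary sample size, and section 9.4 allows for clustering by site in the utilization models and warns that independence often fails for count data. No such allowance is named for the dashboard intervals.

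At stake is how precise the answer to the third main hypothesis (section 9.1) will look. The year-1 summary could carry error bars of about one point, and readers planning roll-out could take that as the precision to expect at other sites.

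**Working it through.** **The plan's own figure.** No interval width, alert-level ICC or design effect is given for the dashboard measures. The only calculation that uses an ICC is the primary sample size, and it reproduces. Inputs (section 9.2): 1.269 events per person-year, a 25% reduction to 0.952, 80% power, two-sided 0.05, ICC 0.05; follow-up is 2 years.
- Per arm before clustering: (1.960 + 0.842)² × (1.269 + 0.952) / (2 × 0.317²) = about 86.6.
- Design effect at 135 per site (1,350/10): 1 + 134 × 0.05 = 7.7.
- Total: 2 × 86.6 × 7.7 = about 1,334, against 1,350 in the plan. Then 1,350/0.85 = about 1,589, against 1,600.

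So 0.05 was applied to ED visits and hospitalizations. Using it for alerts is borrowing.

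**Number of alerts.** Inputs: 1,689 patients, half in the intervention arm (844.5); 365 days; 2 to 3 alerts per 100 patient days; five sites, taken as equal in size.
- 844.5 × 365 × 0.02 = 6,165; × 0.03 = 9,247.
- Per site: 1,233 to 1,849. Per patient: 7.3 to 10.9.

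**Standard interval.** One actionable alert in two, or two in three, gives a proportion of 0.50 to 0.67. Half-width = 1.96 × √(p(1−p)/n), which is 1.0 to 1.2 points.

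**Interval allowing for site.** Design effect DE = 1 + (m − 1) × ICC, with m the alerts per site. The width ratio is √DE with a normal quantile. With t on 4 df it is √DE × 2.776/1.960 = √DE × 1.42. The ratio does not depend on p. Coverage of the standard interval is 2Φ(1.96/√DE) − 1. All ICCs are assumptions.

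| ICC | Between-site SD at p = 0.5 | Ratio, normal | Ratio, t (4 df) | Half-width at p = 0.5, t (4 df) | Actual coverage of nominal 95% |
|---|---|---|---|---|---|
| 0.001 | 1.6 points | 1.5–1.7 | 2.1–2.4 | 2.4–2.6 points | about 75–81% |
| 0.005 | 3.5 points | 2.7–3.2 | 3.8–4.5 | 4.6–4.7 points | about 46–54% |
| 0.01 | 5.0 points | 3.7–4.4 | 5.2–6.3 | 6.4–6.5 points | about 34–41% |
| 0.05 | 11.2 points | 7.9–9.7 | 11.2–13.7 | 14.0 points | about 16–20% |

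**Alert rate.** At 2 per 100 patient days, the Poisson half-width is about ±0.05. If true site rates vary with an assumed CV of 10% or 20%, the ratios with t on 4 df are 5.17 and 10.04, giving about ±0.26 and ±0.50.

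**Time per day.** The unit is the pharmacist-day. With an assumed 250 days per site, the ratio is 1.9 at ICC 0.01 and 3.7 at 0.05, or 2.7 and 5.2 with t on 4 df.

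**Bimonthly looks.** Each holds 205 to 308 alerts per site. The ratio at ICC 0.05 is 3.4 to 4.1, or about 4.7 to 5.7 with t on 4 df.

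**Repeated alerts only, sites held fixed.** At an assumed within-patient ICC of 0.1, DE = 1 + 6.3 × 0.1 = 1.6 up to 1 + 9.9 × 0.1 = 2.0, so the interval is still about 1.3 to 1.4 times too narrow.

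**The case against.** The strongest reply is that these are descriptive summaries of five named sites. Site is then fixed, and variation between sites does not belong in the interval. No stated decision depends on the intervals: the third hypothesis has no numerical threshold, and changes to the dashboard rest on the team's judgement. Section 9.4 gives no interval formula and never says that alerts are independent; that is inferred from the reference to standard statistics and the exclusion of modelling. Alerts are already to be totalled by site.

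Part of this stands. The independence assumption is an inference, though a natural one, and the consequences are limited to secondary descriptive results. The fixed-sites argument does not rescue the intervals, for two reasons. The plan compares the results with expectations formed on the current system and intends them to guide use elsewhere. Repeated alerts within patients also narrow the intervals even when sites are fixed.

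Three stronger readings are tempting, and the documents do not support them:
- **A factor of 5 to 14 as a fact about this trial.** It needs an assumed alert-level ICC of 0.01 to 0.05 together with t on 4 df. At 0.001 to 0.005 the factor is about 2.1 to 4.5.
- **An effective sample size near five.** Five is the number of clusters. The design effects imply about 463 to 475 alerts at ICC 0.01 and about 99 at 0.05.
- **Intervals that reject the expected rate for trivial reasons.** The expectation is a band of two to three alerts. An interval of ±0.05 around an estimate inside that band cannot exclude it.

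**Conclusion.** The concern holds for dashboard intervals calculated in the standard way on pooled alerts. With five sites, one pharmacist per site and 7 to 11 alerts per patient, such intervals overstate precision for any statement beyond these sites. The direction is clear. The size is not known, because it rests on an alert-level ICC that the documents do not give; equal site sizes and full-year follow-up are further simplifications. Even at ICC 0.001, where five pharmacists would have to agree to within an SD of 1.6 points, coverage falls to about 75–81%.

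The large factors belong to the year-1 actionable proportion and should not be carried over to every dashboard measure. Time per day and the bimonthly looks have smaller factors. Acceptance of interventions is a listed objective, but section 9.4 describes no analysis of it, so nothing can be said about its interval. The primary and cost comparisons are not affected.

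**What to change.** In section 9.4, report each dashboard measure by site. Take the overall 95% interval from the five site values (t with 4 df) or from a model with a site random effect. The first option needs no modelling, so the existing exclusion can stay; state whether sites are weighted equally or by volume. Use that interval for actual versus expected rates and for any statement about other VA sites.

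Label any interval that ignores between-site variation as describing these five sites only, and let it still allow for repeated alerts within patients, for example by a patient-clustered variance.

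The cost is a change of SAP wording. Alert totals are already compiled by site, so the site-level alert figures need no new data. The drawback is that the reported intervals become wider.
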